#### 9.4.6.2 CONTINUOUS ENDPOINTS

Summary statistics will be provided by visit and treatment arm. A by-subject listing will be presented for each assessment, by visit. Mixed model for repeated measures (MMRM) method for longitudinal continuous data will be used for testing, with treatment group as main effect, with visit and interaction of treatment by visit as factors, and with baseline values and stratification factor (Hurley Stage at baseline [Stage II or III]) as covariates.

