- Change from Baseline in PGIS at each visit
- Proportion of subjects in each category of Hurley Stage at each visit
- Change from Baseline in Hurley Stage at Weeks 16, 32, and 40
- Proportion of subjects achieving at least a 1-stage improvement in Hurley stage
- Skin tape strip and drainage fluid biomarkers analysis including, but not limited to, IL-36 and Th-17
- Presence of ADAs to imsidolimab
- Serum concentration following imsidolimab administration and other parameters as appropriate will be determined to describe the PK profile of imsidolimab

Methods for analyzing the above categorical and continuous efficacy endpoints will mirror the methods described in [Section 9.4.6.1](#) and [9.4.6.2](#), respectively. ITT analysis set will be used for analysis of exploratory efficacy endpoints.

As further additional exploratory analyses, the primary efficacy endpoint, all secondary efficacy endpoints, and some of the exploratory endpoints will be summarized using the Extension analysis population.

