For PGI-S, PGI-B, HS-PtGA, HS-PGA, and PGI-C, the difference in distribution between the imsidolimab and placebo groups will be compared separately for each treatment group by using a Wilcoxon rank-sum test and Somers' d statistic, which may be interpreted as a generalized risk difference ([Edwardes, 2000](#)). This will be performed over all subjects for each comparison, and within each stratum for Hurley Stage. The difference in distribution between the imsidolimab and placebo groups (stratified by baseline Hurley Stage) will be compared using a Cochran-Mantel-Haenszel test as described in **Section 7.5.2.2**. For PGI-S, PGI-B, HS-PtGA, and HS-PGA, the change from baseline will also be analyzed using an ordinal logistic regression model with treatment and baseline Hurley Stage as categorical covariates. Odds ratios resulting from this model along with 90% CI will be reported. The proportional odds assumption will also be tested, and the corresponding p-value will be reported.

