## APPENDIX 2 SAS CODE FOR STATISTICAL ANALYSES

This section will be completed after examining the existing data and prior to the final signoff of this SAP.

Test	Template SAS Code for Modeling (SAS Version 9.4)
Linear Repeated Measures Analysis of Covariance for the primary endpoint	<pre> PROC MIXED METHOD=REML;   CLASS SUBJECT TRT VISIT BASEHSSTAGE;   MODEL Y = BASE TRT VISIT TRT VISIT/ DDFM=KR SOLUTION   OUTP=OUT;   REPEATED VISIT / TYPE = UN SUBJECT = SUBJECT;   LSMEANS TRT VISIT / PDIFF CL ALPHA=0.1;   ODS OUTPUT LSMEANS=MEANS;   ODS OUTPUT DIFFS=DIFF;   RUN; </pre> 
Where TRT is treatment, VISIT is the study visit number, BASEHSSTAGE is the baseline Hurley Stage, and BASE is the baseline of outcome variable.

General Estimating Equation Repeated Measures with Generalized Logit Transformation	<pre> PROC GENMOD;   CLASS SUBJECT TRT VISIT BASEHSSTAGE;   MODEL Y= BASE TRT VISIT TRT*VISIT / LINK=LOGIT DIST=NEGBIN;   REPEATED SUBJECT=SUBJECT / TYPE=UN;   LSMEANS TRT VISIT / DIFF CL ALPHA=0.1;   ODS OUTPUT LSMEANDIFFS = LSDIFS ESTIMATES=EST   LSMEANS=LSMEANS PARAMETERESTIMATES=PE; </pre> 
Where TRT is treatment, VISIT is the study visit number, BASEHSSTAGE is the baseline Hurley Stage, and BASE is the baseline of outcome variable.

General Estimating Equation Repeated Measures for secondary and exploratory endpoints	<pre> PROC GENMOD;   CLASS SUBJECT TRT VISIT;   MODEL Y = TRT VISIT TRT*VISIT/ DIST=BIN LINK=LOGIT;   REPEATED SUBJECT = SUBJECT /TYPE=UN;   RUN; </pre> 
Where TRT is treatment and VISIT is the study visit number.

Test	Template SAS Code for Modeling (SAS Version 9.4)
Impute Intermittent Missing using the Monte Carlo Markov Chain (MCMC) approach	<pre> PROC MI DATA=data_in SEED=2330710 NIMPUTE=100 OUT=LESION_MONO;   BY BASEHSSTAGE TRT; /*Assuming different treatment, baseline Hurley Stage has different distribution*/   MCMC CHAIN=MULTIPLE IMPUTE=MONOTONE; /*Only impute intermittent missing values*/   VAR AGE BASE AN1 – AN5; /*Impute AN count from Week 4 to Week 16, with age and baseline as covariates*/   RUN; </pre>
Multiple Imputation with FCS Method	<pre> PROC MI MIN=0 ROUND=1;   CLASS BASEHSSTAGE TRT SEX;   FCS REGPMM(AN2 = AN1 AGE SEX TRT BASE BASEHSSTAGE );   FCS REGPMM(AN3 = AN1 AN2 AGE SEX TRT BASE BASEHSSTAGE );   FCS REGPMM(AN4 = AN1-AN3 AGE SEX TRT BASE BASEHSSTAGE );   FCS REGPMM(AN5 = AN1 AN4 AGE SEX TRT BASE BASEHSSTAGE );   VAR AN1 – AN5 AGE SEX TRT BASE BASEHSSTAGE;   RUN; </pre>

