Combine Parameter Estimates for LSmeans	<pre> PROC MIANALYZE DATA=OUTREG;   BY VISIT;   MODELEFFECTS TRT; /* TRT IS THE VARIABLE FOR LS TREATMENT DIFFERENCES */   STDERR TRTERR; /* TRTERR IS THE STANDARD ERROR FOR TREATMENT DIFFERENCES */   RUN; </pre>
Cochran-Mantel-Haenszel ANOVA statistics (row means score)	<pre> PROC FREQ;   TABLES BASEHSSTAGE *TRT*X/CMH2 ALPHA=0.1 SCORE=RANK;   RUN; </pre> 
Where BASEHSSTAGE is randomized Hurley Stage, TRT is treatment, and X is the outcome variable.

Ordinal Logistic Regression using PROC LOGISTIC	<pre> PROC LOGISTIC;   CLASS TRT BASE;   MODEL Y = TRT BASE;   RUN; </pre> 
Where Y is the ordinal outcome variable, TRT is treatment, BASE the baseline of outcome variable.

Exact unconditional CI	<pre> PROC FREQ;   TABLES TRT*X;   EXACT OR;   RUN; </pre>

Test	Template SAS Code for Modeling (SAS Version 9.4)
	Where TRT is treatment, and X is the outcome variable.
Obtaining generalized risk difference	<pre>PROC FREQ;   TABLES TRT*X / ALL LIST MISSING;   TEST SMDCR; RUN;</pre> 
Where TRT is treatment, and X is the outcome variable.

Weighted Kappa and confidence interval	<pre>PROC FREQ;   WEIGHT COUNT;   TABLES BASEHSSTAGE*TRT*X/AGREE ALPHA=0.1; RUN;</pre> 
Where BASEHSSTAGE is Hurley Stage at baseline, TRT is treatment, and X is the outcome variable.

Test of treatment difference for agreement	<pre>PROC FREQ;   TABLES BASEHSSTAGE*TRT*X/CMH2; RUN;</pre> 
Where BASEHSSTAGE is Hurley Stage at baseline, TRT is treatment, and X is the Cicchetti-Allison weight of outcome variable. Cicchetti-Allison weight = 1- abs(CHG)/(k-1), where k = number of categories of the outcome variable.

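### The ordinal logistic model has one covariate set in SAP Section 7.5.3 and another in the Appendix 2 template, possibly with different responses, and neither includes both the baseline score and Hurley Stage

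*SAP*

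**What the plan says.** SAP Section 7.5.3, under the protocol-specified exploratory analyses, covers four ordinal scales here: PGI-S, PGI-B, HS-PtGA and HS-PGA. Its sentence on the model reads: "the change from baseline will also be analyzed using an ordinal logistic regression model with treatment and baseline Hurley Stage as categorical covariates". The SAP asks for odds ratios with 90% confidence intervals and for a test of the proportional odds assumption. The baseline score is not named as a covariate.

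The ordinal logistic block in SAP Appendix 2 has "CLASS TRT BASE" followed by "MODEL Y = TRT BASE", with this key: "Where Y is the ordinal outcome variable, TRT is treatment, BASE the baseline of outcome variable". Hurley Stage does not appear in the block. Elsewhere the same appendix keeps the two variables apart: "BASEHSSTAGE is the baseline Hurley Stage, and BASE is the baseline of outcome variable".

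The protocol does not name an ordinal logistic model. Its model for continuous endpoints (Section 9.4.6.2) is fitted "with baseline values and stratification factor (Hurley Stage at baseline [Stage II or III]) as covariates". For the exploratory endpoints, Section 9.4.7 points back to Sections 9.4.6.1 and 9.4.6.2 in a sentence that begins: "Methods for analyzing the above categorical and continuous efficacy endpoints will mirror the methods described in". SAP Section 8, which lists changes from the protocol, mentions no departure on this point.

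**The concern.** A programmer working from the template and a statistician working from the text would fit different models and report different odds ratios for the same endpoint. Nothing in the SAP says which governs.

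Each version also leaves out something that the plan uses elsewhere. The text omits the baseline score. These are 4- or 5-level scales, so the change a subject can show is limited by where that subject starts, and Hurley Stage does not capture that limit. The template omits the factor on which randomisation was stratified. At stake are the power and the interpretation of four sets of exploratory odds ratios, and the ability to show that the model was fixed before unblinding.

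**Working it through.** The plan states no figure for this model, so the check is a comparison of the two specifications, some counting, and an illustration under stated assumptions.

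**1. Side by side**

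| Element | SAP Section 7.5.3 | SAP Appendix 2 template |
|---|---|---|
| Response | Change from baseline | Y, the ordinal outcome variable |
| Treatment | Yes | Yes (TRT) |
| Baseline score of the outcome | No | Yes (BASE) |
| Baseline Hurley Stage | Yes | No |

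Treatment is the only term in common. BASE cannot be read as Hurley Stage: its key defines it as the baseline of the outcome, Appendix 2 has a separate variable (BASEHSSTAGE) for Hurley Stage, and Hurley Stage is not among the four outcomes. The SAP's own primary model in Section 7.5.1 uses both the baseline value and Hurley Stage.

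**2. How baseline bounds the change**

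Protocol Appendix 3 gives PGI-S four levels, numbered 1 to 4. Appendices 4, 6 and 9 give PGI-B, HS-PtGA and HS-PGA five levels each.

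- Possible values of change: 2 × 4 − 1 = 7 on the 4-level scale; 2 × 5 − 1 = 9 on a 5-level scale.
- Values open to any one subject: 4 of the 7, or 5 of the 9, depending on the baseline level.
- PGI-S Mild (2) at baseline allows changes from −1 to +2. Severe (4) allows −3 to 0. The Mild subject can improve by one level, the Severe subject by three.

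**3. Why the response must be named**

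Suppose the visit score follows a proportional odds model, logit P(score ≤ k) = θ_k − η. For a subject with baseline b, a change of at most c is the same event as a score of at most b + c. Hence logit P(change ≤ c) = θ_(b+c) − η, and the cut-point now depends on b. The text's model has no term to absorb this. Adding BASE to a model for change absorbs it fully only if the cut-points are equally spaced, and never at the ends of the scale, where the probability is 0 or 1. In a linear model with baseline as a covariate, change and score give the same treatment coefficient. In the ordinal model they generally do not.

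**4. Illustration (assumed inputs, except the sample size)**

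The 36 evaluable subjects per arm and the two-sided 0.10 level come from protocol Section 9.2. The 5-level cut-points, a latent treatment effect of 0.6 SD, and Hurley Stage acting only through baseline are assumptions. There were 300 runs per setting, and the template's Y was taken as the visit score.

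| Assumed baseline–outcome correlation | Power, text version | Power, template version | Trials where the two disagree on significance |
|---|---|---|---|
| 0.3 | 74% | 84% | 15% |
| 0.5 | 75% | 84% | 11% |
| 0.7 | 90% | 91% | 4% |

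The simulation error on one power figure near 75% is about √(0.75 × 0.25 / 300) = 0.025.

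A separate simulation with other assumed cut-points and effect size (250 runs per setting) kept change as the response and added the baseline score to the text's model. Power went from 0.52 to 0.67, 0.64 to 0.76 and 0.79 to 0.81 at correlations 0.3, 0.5 and 0.7. The mean standard error of the treatment log odds ratio did not fall: it went from 0.44, 0.45 and 0.46 to 0.46, 0.46 and 0.47. The gain comes from a log odds ratio further from zero, as expected when a prognostic covariate enters a logistic model.

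**The case against.** **The code is only a template.** Appendix 2 says of itself: "This section will be completed after examining the existing data and prior to the final signoff of this SAP". SAP Section 1 calls the plan general guidelines. This lowers the weight. But the SAP is V1.0 with a sign-off date of 16-Aug-2022, so the point by which the appendix was to be completed has passed and the mismatch remains. Treating the text as controlling would not supply the missing baseline score.

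**The analysis is exploratory and supplementary.** This stands. SAP Section 3.3 makes these comparisons exploratory, and the ordinal model comes in addition to other tests.

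**The plan might be said to ignore the stratified randomisation.** The documents do not support that. Hurley Stage is missing only from the template. The text's model includes it, and the same paragraph of Section 7.5.3 plans comparisons within each Hurley stratum and a stratified Cochran-Mantel-Haenszel test.

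**Chance baseline imbalance might be said to drive the text version's odds ratio.** That is too strong. The response is change, so baseline already enters by subtraction. What remains is regression to the mean and the bounds on the scale. In the first simulation the correlation between the text version's z-statistic and the chance baseline imbalance was −0.33, −0.39 and −0.12 across the three assumed correlations, against within ±0.10 for the template version. That is some dependence, not control of the result.

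**Omitting baseline might be said to cost precision.** For a log odds ratio that is the wrong description: the standard error does not shrink when baseline is added. The loss is in power.

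**Conclusion.** The inconsistency is plain and no passage reconciles it. The two specifications share only the treatment term, may model different responses, and estimate different conditional odds ratios even when baseline is perfectly balanced. Neither uses both covariates, although the protocol's continuous-endpoint model and the SAP's primary model do.

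The size cannot be fixed from the documents because they give no baseline–outcome correlation. Under the assumptions shown, the power lost by omitting the baseline score ranges from about 10 to 15 percentage points at a correlation of 0.3 (84 − 74; 67 − 52) to 1 to 2 points at 0.7 (91 − 90; 81 − 79). Adding Hurley Stage changed power little in the first simulation, where it acted only through baseline. The case for it rests on the stratified design and on consistency with the protocol.

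Four exploratory outcomes are affected. Section 7.5.3 names no visit for this model, so its use at every visit is an inference from the endpoint definitions. The primary analysis does not use this model. The point is minor but worth settling before unblinding.

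**What to change.** State one response and one covariate list, identically in SAP Section 7.5.3 and Appendix 2:

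- Response: the ordinal score at the visit, not the change. Say which visits are analysed.
- Covariates: treatment, baseline score of the same outcome, and baseline Hurley Stage.
- Template: `CLASS TRT BASE BASEHSSTAGE; MODEL Y = TRT BASE BASEHSSTAGE;` with Y defined in the key as the visit score.
- If a baseline category is sparse, enter BASE as a numeric score and remove it from the CLASS statement.

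Adding BASEHSSTAGE to the template without defining Y would leave the choice of response open. In the same edit, the block should set the 90% confidence level that the text asks for, since it sets none at present.

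The cost is one SAP sentence and a short code edit. All the data are already collected.

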#### 9.4.4 CONCOMITANT MEDICATION

All medications will be coded using the World Health Organization Drug Dictionary and Anatomical Therapeutic Chemical system. Each medication will be classified as prior medication if it is stopped prior to the first dose of study treatment, or as concomitant medication if it is ongoing at the time of the first dose or is started after the first dose of study treatment. Prior, concomitant, and rescue medications will be summarized descriptively with a by-subject listing.

To handle the issue of rescue medication use, the efficacy data on and after the use rescue medication will be set to missing in the efficacy analysis.

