The Patient Global Impression of change (PGI-C) is a single item, self-administered questionnaire, which asks the patient to rate the change in their symptom severity ("Very much better" to "Very much worse").

For each treatment group, the number of subjects in each response category for the PGI-C will be calculated at each visit specified in the Schedule of Activities in **Section 3.6**. The proportion of such subjects will be calculated for each treatment group at each visit as:

$$\frac{\text{\# of subjects in treatment group in each response category at Week } x}{\text{\# of subjects in treatment group with PGI-C data at Week } x}$$

- **Proportion of subjects achieving much improvement according to the PGI-C at each visit**

For each treatment group, the number of subjects achieving improvement (“Much better”, or ‘Very much better”) according to the PGI-C will be calculated at each visit specified in the Schedule of Activities in **Section 3.6**. The proportion of such subjects will be calculated for each treatment group at each visit as:

$$\frac{\text{\# of subjects in treatment group in either improvement response category at Week } x}{\text{\# of subjects in treatment group with PGI-C data at Week } x}$$

- **Proportion of subjects achieving improvement according to the PGI-C at each visit**

For each treatment group, the number of subjects achieving improvement (“A little better”, “Much better”, or ‘Very much better”) according to the PGI-C will be calculated at each visit specified in the Schedule of Activities in **Section 3.6**. The proportion of such subjects will be calculated for each treatment group at each visit as:

$$\frac{\text{\# of subjects in treatment group in any improvement response category at Week } x}{\text{\# of subjects in treatment group with PGI-C data at Week } x}$$

- **Proportion of subjects in each response category for the PGI-B at each visit**

For each treatment group, the number of subjects in each response category for the PGI-B will be calculated at each visit specified in the Schedule of Activities in **Section 3.6**. The proportion of such subjects will be calculated for each treatment group at each visit as:

$$\frac{\text{\# of subjects in treatment group in each response category at Week } x}{\text{\# of subjects in treatment group with PGI-B data at Week } x}$$

- **Change from Baseline in PGI-B at each visit**

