- **Proportion of subjects achieving “A little bothered” or “Not at all bothered” for the PGI-B at each visit**

For each treatment group, the number of subjects “A little bothered” or “Not at all bothered” for the PGI-B will be calculated at each visit specified in the Schedule of Activities in **Section 3.6**. The proportion of such subjects will be calculated for each treatment group at each visit as:

$$\frac{\text{\# of subjects in treatment group achieving either “A little bothered” or “Not at all bothered” category at Week } x}{\text{\# of subjects in treatment group with PGI-B data at Week } x}$$

- **Proportion of subjects in each response category for the PGI-S at each visit**

The Patient Global Impression of Severity (PGI-S) is a single-item question, which asks the patient to rate the current severity of the HS (“No Activity” / “Clear Skin”, “Mild”, “Moderate”, and “Severe”).

For each treatment group, the number of subjects in each response category for the PGI-S will be calculated at each visit specified in the Schedule of Activities in **Section 3.6**. The proportion of such subjects will be calculated for each treatment group at each visit as:

$$\frac{\text{\# of subjects in treatment group in each response category at Week } x}{\text{\# of subjects in treatment group with PGI-S score at Week } x}$$

- **Change from Baseline in PGI-S at each visit**
- **Proportion of subjects achieving “Mild” or “No activity” / “Clear skin” for the PGI-S at each visit**

For each treatment group, the number of subjects with either “Mild” or “No activity” / “Clear Skin” response category for the PGI-S will be calculated at each visit specified in the Schedule of Activities in **Section 3.6**. The proportion of such subjects will be calculated for each treatment group at each visit as:

$$\frac{\text{\# of subjects in treatment group with either "Mild" or "No activity" / "Clear Skin" response category at Week } x}{\text{\# of subjects in treatment group with PGI-S score at Week } x}$$

- **Proportion of subjects in each category of Hurley Stage at each visit**

The Hurley system describes 3 clinical stages of HS (Stage I, II, and III). The Hurley stage at a given visit will be determined by the site as the greatest Hurley Stage observed from all involved anatomical regions.

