# 7. STATISTICAL ANALYSIS

## 7.1 Data Handling Rules and Definitions, Including Handling of Missing Data

Except where specified, all continuous variables will be summarized with descriptive statistics (the number of non-missing values, mean, standard deviation, first and third quartiles, median, minimum, and maximum). Where data have been logarithmically transformed for analysis, the summary statistics on the back-transformed data will include the geometric mean (calculated as  $\exp(m)$ ), where  $m$  is the mean of the data on the log scale) and the coefficient of variation (calculated as  $100\sqrt{[\exp(s^2)-1]}$ , where  $s$  is the standard deviation of the data on the log scale). All categorical variables will be summarized with frequency counts and percentages. Tabulations will be provided based on all subjects combined, as well as separately by treatment group.

Missing data will be maintained as missing in the analysis datasets, unless specified otherwise. For variables where missing data are imputed, the analysis dataset will contain a new variable with the imputed value and the original variable value will be maintained as missing.

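### The SAP's Somers' d template treats a missing global-scale score as a valid lowest category, so where missing rows are in the input the estimate mixes scores with missingness

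*SAP*

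**What the plan says.** SAP 7.5.3 sets out the comparison: "For PGI-S, PGI-B, HS-PtGA, HS-PGA, and PGI-C, the difference in distribution between the imsidolimab and placebo groups will be compared separately" for each active arm, using a "Wilcoxon rank-sum test and Somers' d statistic, which may be interpreted as a generalized risk difference". That section gives no rule for a missing score.

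SAP Appendix 2, in the row on obtaining the generalized risk difference, gives the only Somers' d code: "TABLES TRT*X / ALL LIST MISSING", followed by a request for the Somers' d (C|R) test. The other PROC FREQ templates in that appendix (CMH, exact interval, weighted kappa, agreement test) do not carry the MISSING option.

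Two passages bear on whether missing values reach this code:
- SAP 7.1: "Missing data will be maintained as missing in the analysis datasets, unless specified otherwise".
- Protocol 9.4.4: "the efficacy data on and after the use rescue medication will be set to missing in the efficacy analysis".

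For the category proportions on these same scales, SAP 6.2.4 uses subjects with data as the denominator, for example "subjects in treatment group with PGI-S score at Week" x for PGI-S and "of subjects in treatment group with PGI-C data at Week" x for PGI-C.

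**The concern.** In PROC FREQ, MISSING on the TABLES statement turns a missing value into an ordinary level that enters every test and measure of association. A numeric missing value sorts below all numbers. The direction of the scales then decides what that means:

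- HS-PGA runs from 0 (inactive) to 4 (severe), and HS-PtGA from 0 (not at all) to 4 (extremely).
- PGI-S numbers its no-activity option 1, and PGI-C numbers its very-much-better option 1.
- PGI-B (Protocol Appendix 4) is listed best-first but has no numeric codes.

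On the first four scales a subject with a missing score is ranked as doing better than the best possible answer. If post-rescue scores are set to missing, that includes subjects whose disease was bad enough to need intervention. The quantity estimated is then no longer a difference in score distributions but a blend of scores and missingness. It can move in either direction, depending on which arm has more missing data.

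**Working it through.** **Inputs from the documents.** 40 subjects randomized per arm; 10% total dropout by Week 16, so 40 × 0.90 = 36 remaining (Protocol 9.2, SAP 3.5); two-sided 0.10 level (Protocol 9.4.1, SAP 7.5). The documents give no figure for Somers' d, so there is none to reproduce.

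**Assumed inputs.** Missing rates by arm, and a four-category scale with lowest best. Placebo probabilities are 0.1/0.3/0.4/0.2. The same probabilities are used on imsidolimab for the no-effect case, and 0.2/0.4/0.3/0.1 for an effect.

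**Formula.** Let m1 and m0 be the missing rates on imsidolimab and placebo, and let positive d favour imsidolimab. Take one subject from each arm:
- Both observed, probability (1−m1)(1−m0): contributes d_observed.
- Only the imsidolimab score missing, m1(1−m0): counted as a win for imsidolimab.
- Only the placebo score missing, m0(1−m1): counted as a loss.
- Both missing: a tie.

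The second and third terms net to m1(1−m0) − m0(1−m1) = m1 − m0. Hence

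d with MISSING = (1−m1)(1−m0) × d_observed + (m1 − m0).

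**Check on one table.** Identical score distributions, 8 of 40 missing on imsidolimab and 2 of 40 on placebo: the formula gives 0.20 − 0.05 = 0.15. Direct calculation gives 0.15 with MISSING and 0 without.

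**Assumed effect.** Imsidolimab better: 0.2×0.9 + 0.4×0.6 + 0.3×0.2 = 0.48. Worse: 0.4×0.1 + 0.3×0.4 + 0.1×0.8 = 0.24. So d_observed = 0.48 − 0.24 = 0.24.
- Missing 10% v 10%: 0.81 × 0.24 + 0 = 0.19.
- Missing 10% imsidolimab v 20% placebo: 0.72 × 0.24 − 0.10 = 0.07.
- Missing 10% v 30%: 0.63 × 0.24 − 0.20 = −0.05.

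**Rejection rates by simulation**, 40 per arm, two-sided 0.10:

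| Case | Missing, imsidolimab v placebo | With MISSING | Scores only |
|---|---|---|---|
| No effect | 10% v 10% | 10–11% | about 11% |
| No effect | 12.5% v 7.5% | 13–14% | about 11% |
| No effect | 15% v 5% | 22% | about 11% |
| d = 0.24 | 10% v 10% | about 48% | about 59% |
| d = 0.24 | 10% v 20% | about 16% | about 58% |

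Swapping the rates between arms reverses the sign of the bias under no effect and leaves the rejection rate the same.

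**The case against.** Several points on the other side have force.

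- **The input rows are not specified.** SAP 7.1 keeps missing values missing; it does not say that a row is created for a visit that never took place. The template names no dataset, filter or visit. If the input held only subjects with a score, MISSING would change nothing. This stands as a condition on the finding. The SAP restates the blanking of post-rescue data only for the primary estimand, although the protocol rule covers efficacy data generally. Rescue is allowed only from Week 8 (Protocol 6.6), so it cannot cause missing scores at Week 4.
- **PGI-B.** With no codes in Protocol Appendix 4, the claim that missing ranks best there is conditional. This stands.
- **Size.** The plan supports 10% total dropout and no imbalance. Larger distortions, including the sign reversal at 10% v 30%, need more missing data than that, concentrated in one arm. This stands.
- **Template status.** Appendix 2 says it was to be completed before final signoff, and no text asks for missing as a category. But the line is in V1.0, and nothing in SAP 7.5.3 overrides it.
- **Limited reach.** SAP 7.5.3 also applies a Wilcoxon test and a stratified CMH test to these scales, and ordinal logistic regression to four of them, so a distorted Somers' d could be seen to disagree. This limits the consequence but does not make the code right.

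A reader might also infer that the code reverses the nonresponse rule in Protocol 9.4.6.1. That rule covers Yes/No criteria; it does not say how to rank a missing score on an ordinal scale, so the documents do not support calling it a direct contradiction. The firm inconsistency is with the SAP 6.2.4 denominators and the sibling templates.

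**Conclusion.** Wrong as written. If rows with missing scores enter the template, which SAP 7.1 and Protocol 9.4.4 suggest but do not establish, a missing HS-PGA, HS-PtGA, PGI-S or PGI-C score outranks the best answer. The same holds for PGI-B if it is coded best-first.

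Equal missingness preserves the test level and costs power through a smaller d. Unequal missingness shifts d by m1 − m0 on top of that shrinkage. At the plan's 10% average, modest imbalance (12.5% v 7.5%) raises false rejection only slightly, and 15% v 5% about doubles it. These sizes rest on the assumed split by arm and the assumed category distributions.

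It is tempting to read this as saying that an inert drug will show benefit, or that a real benefit will be cancelled. The documents predict neither, because they give no missing rates by arm.

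The effect is confined to the exploratory Somers' d results. The primary MMRM, the secondary endpoints, and the CMH and ordinal logistic analyses are untouched.

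**What to change.** In SAP Appendix 2, delete MISSING and LIST and use `TABLES TRT*X / MEASURES CL ALPHA=0.1; TEST SMDCR;`, run on subjects with a score at the visit. LIST should go because it leaves doubt whether the statistics would be produced as written. ALPHA=0.1 supplies the 90% interval that SAP 7.5 calls for and the present line omits.

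Add one sentence to SAP 7.5.3 stating that the comparison uses subjects with a score at the visit, in line with SAP 6.2.4, and record how PGI-B is coded.

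A sensitivity run with missing scores placed in the worst category is optional. It would extend the Yes/No nonresponse rule of Protocol 9.4.6.1 rather than apply it, and should be described that way.

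The cost is one line of code and a sentence or two of text. The downside is that fewer subjects enter the comparison, and their results describe those with observed scores only.
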